8.5 Stopping Criteria

The study will be halted, and the risk to other subjects evaluated if any of the following criteria are met:

- A serious adverse reaction (ie a serious AE considered at least possibly related to the IMP administration) in one subject.

- Severe non-serious adverse reactions (ie severe non-serious AE considered as, at least possibly related to the IMP administration) in two subjects in the same cohort, independent of within or not within the same system organ class.

Relatedness will be determined by the investigator.

If the study is halted, a temporary halt will be submitted to the Medicines and Healthcare products Regulatory Agency (MHRA) and ethics committee (EC) in the form of a substantial amendment. The study may be resumed or terminated; however, it will not be resumed until a further substantial amendment to resume the study is submitted and approved by MHRA and EC.

The ARSAC Practitioner will also be informed of the temporary halt.

8.6 Study Termination

After the start of protocol activities but prior to the commencement of dosing, the study may be terminated by the sponsor and investigator without consultation with the MHRA, EC and ARSAC practitioner or ARSAC. The end of the trial must be notified to the MHRA and EC immediately and at the latest within 15 days after the study is terminated, clearly explaining the reasons. A description of any follow-up measures taken for safety reasons if applicable, will also be provided. The ARSAC Practitioner and ARSAC will also be notified within an appropriate timeframe.

If the study is abandoned prior to commencement of any protocol activities, the PI or sponsor must notify the EC, MHRA, ARSAC practitioner and ARSAC (if ARSAC research application has been submitted or approved) in writing outlining the reasons for abandonment of the trial.

Once exposure to ionising radiation has begun, the study will be completed as planned unless the following criteria are satisfied that require a temporary halt or early termination of the study.

- The occurrence of serious or severe adverse event(s), as defined in [Section 8.5](#), if considered to be related to the IMP, as defined in [Section 14.2](#).
- New information regarding the safety of the IMP that indicates a change in the risk/benefit profile for the compound, such that the risk/benefit is no longer acceptable for subjects participating in the study.
- Significant violation of Good Clinical Practice (GCP) that compromises the ability to achieve the primary study objectives or compromises subject safety.

If any of the above occurs, the study will be terminated if careful review of the overall risk/benefit analysis described in [Section 6.4](#) demonstrates that the assumptions have changed and that the overall balance is no longer acceptable. In these circumstances termination can only take place with the agreement of the investigator and sponsor. The MHRA, EC, ARSAC practitioner and ARSAC will be informed of study termination.

If it becomes necessary to consider termination of the study on the dosing day, dosing may be suspended pending discussion between the investigator, sponsor and ARSAC practitioner. Dosing will be stopped immediately on safety grounds.

The study may be terminated or suspended at the request of the MHRA or EC.

8.7 Treatment Allocation

This is an open-label, non-randomised study, therefore a randomisation schedule will not be produced. A treatment allocation will be produced prior to dosing with IMP, which will dictate the order in which the treatments should be administered to each subject. The treatment allocation will be retained in the Investigator Site File.

8.7.1 Subject Numbers

Subject numbers will be allocated on the morning of dosing according to the code 001 to 006 using the lowest number available.

8.7.2 Blinding

This is an open-label, non-randomised study and therefore blinding is not required.

9 Selection of Subjects

Quotient Sciences must have a full medical history from each subject's general practitioner (GP) within the last 12 months, prior to enrolment for the study.

Subjects will be recruited from the Quotient Sciences panel or by direct advertising to the public.

Before subjects are admitted to the clinical unit, The Over Volunteering Prevention System will be checked to ensure that each subject has not participated in a study at another site within at least 90 days of the dosing date.

9.1 Informed Consent

Subjects will be provided with a written explanation of the study at least the day before the screening visit. A physician or nurse will explain to each subject the nature of the study, its purpose, expected duration and the benefits and risks involved in study participation. Subjects will be informed that, for safety reasons, brief details of their involvement in the study may be revealed to other units and companies that carry out clinical studies in the local area. Subjects will then be given the opportunity to ask questions and will be informed of their right to withdraw from the study without prejudice. After this explanation and before entering the study, the subject will voluntarily sign an informed consent form (ICF). Until written consent has been obtained from the subject no study specific procedure or investigation will be performed. If an amendment is made to the participant information sheet (PIS), participants will be re-consented to the most current version of the ICF(s) where appropriate.

9.2 Inclusion Criteria

1. Healthy males
2. Age 30 to 65 years of age at the time of signing informed consent
3. Body mass index (BMI) of 18.0 to 30.0 kg/m² as measured at screening
4. Must be willing and able to communicate and participate in the whole study
5. Must have regular bowel movements (ie average stool production of ≥ 1 and ≤ 3 stools per day)
6. Must provide written informed consent
7. Must agree to adhere to the contraception requirements defined in [Section 9.4](#)

Inclusion criteria 1, 4, 5, 6 and 7 from the list above will be re-assessed at admission/pre-dose.

9.3 Exclusion Criteria

1. Subjects who have received any IMP in a clinical research study within the 90 days prior to Day 1
2. Subjects who are study site employees, or immediate family members of a study site or sponsor employee
3. Subjects who have previously been enrolled in this study
4. History of any drug or alcohol abuse in the past 2 years
5. Regular alcohol consumption in males >21 units per week (1 unit = ½ pint beer, or a 25 mL shot of 40% spirit, 1.5 to 2 Units = 125 mL glass of wine, depending on type)
6. A confirmed positive alcohol breath test at screening or admission
7. Current smokers and those who have smoked within the last 12 months. A confirmed breath carbon monoxide reading of greater than 10 ppm at screening or admission
8. Current users of e-cigarettes and nicotine replacement products and those who have used these products within the last 12 months
9. Subjects with pregnant or lactating partners
10. Radiation exposure, including that from the present study, excluding background radiation but including diagnostic X-rays and other medical exposures, exceeding 5 mSv in the last 12 months or 10 mSv in the last 5 years. No occupationally exposed worker, as defined in the Ionising Radiation Regulations 2017, shall participate in the study
11. Subjects who do not have suitable veins for multiple venepunctures/cannulation as assessed by the investigator or delegate at screening
12. Clinically significant abnormal clinical chemistry, haematology or urinalysis as judged by the investigator (laboratory parameters are listed in [Appendix 1](#)). Subjects with Gilbert's Syndrome are allowed
13. Confirmed positive drugs of abuse test result (drugs of abuse tests are listed in [Appendix 1](#))
14. Positive hepatitis B surface antigen (HBsAg), hepatitis C virus antibody (HCV Ab) or human immunodeficiency virus (HIV) results
15. Evidence of renal impairment at screening, as indicated by an estimated creatinine clearance of <80 mL/min using the Cockcroft-Gault equation
16. History of clinically significant cardiovascular, renal, hepatic, chronic respiratory or gastrointestinal disease, neurological or psychiatric disorder, as judged by the investigator
17. Serious adverse reaction or serious hypersensitivity to any drug or the formulation excipients
18. Presence or history of clinically significant allergy requiring treatment, as judged by the investigator. Hay fever is allowed unless it is active
19. Donation or loss of greater than 400 mL of blood within the previous 3 months
20. Subjects who are taking, or have taken, any prescribed or over-the-counter drug (other than 4 g of paracetamol per day), herbal remedies, vitamin B5 or dietary supplements containing lipoic acid in the 14 days before IMP administration (see [Section 11.4](#)). Exceptions may apply on a case by case basis, if considered not to interfere with the objectives of the study, as determined by the PI
21. Subjects who have had any intake of biotin (including as a nutritional supplement) in the 14 days before IMP administration
22. Failure to satisfy the investigator of fitness to participate for any other reason

Exclusion criteria [6](#), [7](#), [9](#), [10](#), [12](#), [13](#), [18](#), [19](#), [20](#), [21](#) and [22](#) from the list above will be re-assessed at admission/pre-dose.

Healthy subjects who do not meet the inclusion/exclusion criteria for the study will not be enrolled.

9.4 Contraception

Male subjects who are sexually active with a partner of child bearing potential must use, with their partner, a condom plus an approved method of effective contraception from the time of informed consent until 90 days after IMP administration.

The following methods are acceptable:

- Partner's use of combined (oestrogen and progestogen-containing) hormonal contraception associated with inhibition of ovulation:
 - oral
 - intravaginal
 - transdermal
- Partner's use of progestogen-only hormonal contraception:
 - oral
 - injectable/implantable
 - intrauterine hormone-releasing system
- Partner's use of intrauterine device
- Surgical sterilisation (for example, vasectomy or partner's bilateral tubal occlusion)
- Partner's use of female cap or diaphragm or sponge with spermicide (double barrier)

Alternatively, sexual abstinence is considered a highly effective method only if defined as refraining from heterosexual intercourse during the entire period of risk associated with the study treatments. The reliability of sexual abstinence needs to be evaluated in relation to the duration of the clinical trial and the preferred and usual lifestyle of the subject.

These contraception requirements are aligned with guidance issued by the Heads of Medicines Agency: Clinical Trials Facilitation Group [\[12\]](#).

9.4.1 Exposure to Sexual Partners During the Study

There is a significant risk of drug exposure through the ejaculate (which also applies to vasectomised males) that might be harmful to sexual partners (both male and female), including pregnant partners of male subjects. Therefore, a condom should be used by all male subjects throughout the study and for 90 days after IMP administration.

9.4.2 Sperm Donation

Male subjects should not donate sperm for the duration of the study and for 90 days after IMP administration.

9.5 Pregnancy

Subjects will be instructed that if their partner becomes pregnant during the study this should be reported to the investigator. The investigator should also be notified of pregnancy occurring during the study but confirmed after completion of the study. In the event that a subject's partner is subsequently found to be pregnant after the subject is included in the study, then consent will be sought from the partner and, if granted, any pregnancy will be followed and the status of mother and/or child will be reported to the sponsor after delivery.

A pregnancy notification form and follow-up will be completed.

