Based on the safety profiles of MD1003 in rats and dogs following repeated administrations, there is no identified toxicity associated with MD1003 using doses resulting in up to 8-fold the plasmatic exposure corresponding to the MS trial doses of 100 mg orally 3 times daily (TID). MD1003 did not reveal any untoward effect on the CNS, respiratory, cardiovascular, hepatic or renal functions. In several studies, MD1003 did not demonstrate genotoxic potential. This combined with the absence of genotoxicity or carcinogenicity in literature reports suggest that biotin is unlikely to present a risk for carcinogenicity. No carcinogenicity studies have been conducted with MD1003, but a 2-year study in rats and a 6-month study in transgenic rasH2 mice are ongoing. A teratogenic effect of MD1003 was observed in pregnant rabbits at a dose equivalent to twice the exposure in humans in the absence of maternal toxicity. No teratogenic effect was observed in rats. However, the risk of teratogenicity observed in rabbits cannot be excluded in humans at the MD1003 therapeutic dose. Oral doses of MD1003 did not result in epithelial irritation and is not expected to have allergic potential.

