8.1 Study Plan

[figure not shown]
This is a single-centre, open-label, non-randomised, single oral dose study in healthy male subjects. It is planned to enrol 6 subjects to ensure 4 evaluable subjects.

Each subject will receive a single oral administration of a capsule containing 100 mg MD1003 and NMT 2.22 MBq (approximately 60.0 µCi) [¹⁴C], in the fasted state.

The study design is presented in [Figure 1](#). Subjects will be screened to participate in the study up to 28 days before dosing. Subjects will be admitted to the clinical unit on the evening of Day -1 prior to IMP administration.

Subjects will be dosed on the morning of Day 1 following an overnight fast and will remain resident in the clinical unit until up to 168 h after dosing (up to Day 8). It is planned that subjects will be released as a group when all subjects have achieved a mass balance cumulative recovery of >90% or if <1% of the dose administered has been collected in urine and faeces within 2 separate consecutive 24 h periods. This may result in the subjects being discharged as a group prior to completion of the planned residency period. Once the discharge criteria or the planned residency period has been achieved, collection of all samples (blood, urine and faeces) will be stopped and the subjects will undergo discharge assessments. If the mass balance criteria have not been met by all subjects by Day 8, the residency period for the subjects not achieving the release criteria may be extended up to a maximum of an additional 48 h (up to Day 10) for further collection of urine and/or faeces. If the release criteria have still not been met by Day 10, or if any additional residency is not considered appropriate or necessary, then home collections of urine and/or faeces may be requested at the discretion of the investigator for individual subjects.

Figure 1 Study Sequence

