18.6 Declaration of the End of the Study

The end of the study is defined as the last visit of the last subject (eg discharge). Any changes to this definition will be notified as a substantial amendment (see [Section 17.1](#)).

The EC and MHRA should be notified in writing of the conclusion of the study within 90 days of the end of the study, or within 15 days if the study is terminated early, clearly explaining the reasons for the termination.

ARSAC and the ARSAC Practitioner will also be notified of the end of trial or early termination of the trial in writing within an appropriate timeframe.

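### Section 9.5 asks subjects to report a partner pregnancy only if it arises during the study, but the protocol's own reproductive precautions run to 90 days after dosing

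*Protocol*

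**What the plan says.** **The instruction to report.** Protocol section 9.5 has two sentences on notification. The first reads "Subjects will be instructed that if their partner becomes pregnant during the study this should be reported to the investigator". The second reads "The investigator should also be notified of pregnancy occurring during the study but confirmed after completion of the study". The second allows a later date of confirmation, but the pregnancy must still have arisen within the study.

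**Follow-up.** The third sentence of 9.5 concerns a partner who is "subsequently found to be pregnant after the subject is included in the study, then consent will be sought from the partner". With that consent, the pregnancy is followed and the outcome goes to the sponsor after delivery. No end date is attached.

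**The end of the study.** Section 18.6 takes this to be the last visit of the last subject, and gives discharge as the example. Under section 8.1, residency lasts up to 168 h after dosing (Day 8). The group may be released earlier if recovery criteria are met, residency may be extended by 48 h to Day 10, and home collections may be requested after that.

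**The precautions.** Section 9.4 requires "a condom plus an approved method of effective contraception from the time of informed consent until 90 days after IMP administration". Sections 9.4.1 (condom use) and 9.4.2 (sperm donation) also run to 90 days after dosing. The background is in section 5.3.1: "the risk of teratogenicity observed in rabbits cannot be excluded in humans at the MD1003 therapeutic dose". Section 5.3.2.1 names teratogenicity as a potential risk.

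**The concern.** The protocol sets two different periods for the same risk. Its precautions treat the 90 days after dosing as the time in which conception, or exposure of a partner, matters. Its request to be told about a pregnancy stops when the study stops, roughly a week after dosing.

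Take a conception on Day 30 after a contraceptive failure. It lies well inside the period that 9.4 guards, yet it meets neither notification sentence of 9.5. Subjects are resident in the unit for most of the time the instruction does cover after dosing, so conception is least likely then.

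What is at stake is safety information: an exposed pregnancy that the protocol undertakes to follow may not reach the site, because nobody has asked the subject to mention it.

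**Working it through.** The protocol gives no figure for this point, so there is none to reproduce. The check has two parts: whether the study can be read as including the 90 days, and how large the mismatch is if it cannot.

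**Part 1: are the two periods the same?**

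- Sections 9.4.1 and 9.4.2 each name the study and the 90 days after dosing as two items joined by *and*. If the study already contained the 90 days, the second item would be redundant.
- The synopsis estimates about 6 weeks (42 days) from screening to the end of the study. Ninety post-dose days alone exceed that.
- Section 18.6 gives discharge as its example of the last visit, and sections 14.1 and 14.3 record adverse events only until discharge.

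The protocol's own usage therefore keeps the 90 days outside the study.

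**Part 2: the size of the mismatch**

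Inputs:

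- Risk window after dosing: 90 days (9.4, 9.4.1, 9.4.2).
- Planned discharge: 168 h ÷ 24 = 7 days after dosing, Day 8 (8.1).
- Longest residency: (168 + 48) h = 216 h; 216 ÷ 24 = 9 days after dosing, Day 10 (8.1).

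Formula: share outside the instruction = (90 − days from dosing to study end) ÷ 90.

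| Study end | Days after dosing | Days outside | Share of 90 |
|---|---|---|---|
| Day 8 (planned) | 7 | 90 − 7 = 83 | 83/90 = 92.2% |
| Day 10 (longest residency) | 9 | 90 − 9 = 81 | 81/90 = 90.0% |

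**Sensitivity**

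- *Later study end.* Assume a full 28-day screening period and the full 6 weeks. The study then ends 42 − 28 = 14 days after dosing, and the share is (90 − 14)/90 = 76/90 = 84.4%.
- *Window counted from consent, as 9.4 words it.* Assume consent 28 days before dosing, so the window is 28 + 90 = 118 days. The share is 83/118 = 70.3% for Day 8 and 81/118 = 68.6% for Day 10. The days before dosing carry no drug exposure, so the 90-day denominator is the more relevant one.

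These are shares of days, not of pregnancies expected or missed.

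**After the fix.** If the instruction ran to 90 days after dosing, no day would fall outside it. Reporting could then last up to 118 days (118 ÷ 7 = 16.9 weeks) from screening, against about 6 weeks for the study. It therefore has to be defined separately from the study.

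**The case against.** The strongest reply is the third sentence of 9.5. It has no end date, it covers any partner pregnancy found after inclusion, and a Day 30 conception fits its words. A reader might infer from the first two sentences that all pregnancy reporting and follow-up stops at discharge, so that about 90% of the window is unmonitored. The third sentence rules that reading out. What it leaves open is how the site comes to know: it starts once a pregnancy has been found, and it asks nothing of the subject. Section 14.4.1 (congenital anomaly as a serious event) and section 16.1 (serious events after completion) depend in the same way on the site being told.

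A reader might also infer that there is no contact after discharge and that the site could not learn of a pregnancy. The documents do not establish this. The schedule table in Appendix 2 is not in the available text, section 8.3 allows a subject's last contact to be a phone call, and section 14.5.6 mentions follow-up assessments. Section 10.3.4 gives every subject a card with the investigator's number and a 24/7 on-call contact. The consent documents are not available either, so what they say about reporting is unknown. A route to the site exists; the protocol lacks an instruction to use it through the 90 days.

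A third temptation is to quote 87/90 = 97%, taking Day 4 as the earliest discharge. Day 4 is the 72 h evaluability criterion in section 8.4. The protocol allows early group release but fixes no earliest day. Nor is Day 10 a firm upper limit, since home collections have no stated end.

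Finally, the practical weight is limited: six men, one dose, and a condom plus a second method required. That stands, and it bears on priority rather than on whether the text is consistent.

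**Conclusion.** The point holds as a mismatch between the reporting instruction in 9.5 and the precaution window in 9.4 to 9.4.2. A conception between the end of the study and 90 days after dosing falls under no instruction to report. That gap is 90% to 92% of the post-dose days on the residency limits in 8.1, and 84% if the study runs to 14 days after dosing. Section 9.5 is not closed at discharge: its follow-up sentence is open-ended, but no matching request for notification and no stated period go with it.

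The figures assume that the last visit is discharge from the unit and that all subjects are dosed on the same day, as planned group release suggests. Home collections that carried a last visit beyond Day 10 would lower the share; early group release would raise it.

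This is worth correcting because teratogenicity is a risk the protocol itself names and the correction is nearly free. It does not touch the sample size, any endpoint or any analysis.

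**What to change.** Reconcile 9.5 with 9.4, using the window the protocol already has:

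1. In both notification sentences of 9.5, replace the reference to the study with the period from informed consent to 90 days after IMP administration. The period should begin at consent. If it began at dosing, it would drop pregnancies arising between consent and dosing, which the present wording covers and the 9.4 window includes.
2. State in 9.5 that reporting, and follow-up to delivery, continue after the end of study defined in 18.6. That definition can then stay as it is.
3. Make sure the information given at discharge carries the same instruction and points to the contact card in 10.3.4. If the participant information already says this, only the protocol text needs to change.

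The cost is two or three sentences, with no added visit, sample or procedure. The site must keep a reporting route open for 90 days after dosing.
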